8.9.2 Test-Retest Reliability

The test-retest reliability of the double vital capacity 35% CO2/65% O2 in healthy subjects who have previously been tested sensitive to the panicogenic effects of the CO2 challenge, which is assessed with the Panic Symptoms List-IV (PSL-IV), VAS Discomfort, and VAS subjective anxiety and fear.

Test-retest reliability will be analyzed with repeated measures mixed model ANCOVA with challenge number as fixed factor, subject as random factor and baseline as covariate.

8.9.3 Occurrence of tolerance after repeated exposure

The occurrence and intensity of PAs in CO2 sensitive healthy subjects caused by a double (and single) vital capacity inhalation of 35% CO2/65% O2.

For the occurrence of PAs repeated measures logistic regression will be used with challenge number as fixed factor and subject as random factor.

The intensity of PAs will be analyzed with repeated measures mixed model ANCOVA with challenge number as fixed factor, subject as random factor and baseline as covariate.

8.9.4 Stable trait phenomenon

The occurrence and intensity of PAs in CO2 sensitive healthy subjects caused by a double (and single) vital capacity inhalation of 35% CO2/65% O2 now and some time ago.

For the occurrence of PAs repeated measures logistic regression will be used with challenge number as fixed factor and subject as random factor.

The intensity of PAs will be analyzed with repeated measures mixed model ANCOVA with challenge number as fixed factor, subject as random factor and baseline as covariate.

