1.2.5 Primary endpoint

The primary endpoint will be based on the PSL-IV total Score, VAS Fear, and VAS Discomfort as these are the endpoint to objectify the panicogenic effect of the CO2 Challenge. This study aims to illuminate the primary endpoints of the following three objectives as follows:

- 1. The objective is to discern and contrast the frequency and intensity of panic attacks induced by a single vs. a double vital capacity inhalation of 35% CO2/65% O2. We will accomplish this by quantifying the difference in pre- and post-CO2 challenge metrics namely PSL-IV, VAS Fear, and VAS Discomfort. The goal is to reveal any statistically significant distinctions in the frequency and intensity of panic reactions between these two inhalation scenarios.
- 2. The objective is to determine whether the test-retest outcomes of double vital capacity 35% CO2/65% O2 inhalation remain consistent in CO2-sensitive healthy volunteers. We will accomplish this by quantifying the difference in pre- and post-CO2 challenge metrics namely PSL-IV, VAS Fear, and VAS Discomfort. The goal is to identify whether the panic response stays steady across repeated exposures, thus measuring the consistency of the test-retest.
- 3. The objective is to scrutinize the consistency and reliability of panic reactions induced by the repeated inhalation of double vital capacity 35% CO2/65% O2 in CO2-sensitive, healthy volunteers. We will accomplish this by quantifying the difference in pre- and post-CO2 challenge metrics specifically PSL-IV, VAS Fear, and VAS Discomfort, between the initial and subsequent inhalation tests. The goal is to determine whether repeated exposures yield statistically significant consistency in the frequency and intensity of panic responses among the study participants.
- 4. The objective is to discern and contrast the persistence of sensitivity to the panicogenic effects of CO2 in healthy participants, previously identified as CO2-sensitive, over an extended period. We plan to accomplish this by quantifying the variation in pre- and post-CO2 challenge metrics, specifically PSL-IV, VAS Fear, and VAS Discomfort, between these two timepoints initial assessment and years later. The aim is to establish whether there exist statistically significant distinctions in the frequency and intensity of panic reactions over time, indicating a maintained sensitivity or alteration to the CO2 challenge.

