4.2 Inclusion criteria

- 1. Healthy male or female aged between 18 and 65 years (inclusive) at screening who have been demonstrated to be sensitive to the panicogenic effects of the CO2 challenge in previous studies.
- 2. Sensitivity to the fear-inducing effects of 35% CO2 double-breath inhalation is defined as an increase from pre-CO2 to post-CO2 challenge in the following: PSL-IV total scores ≥4 with at least 1-point increase for at least 4 of the symptoms specified in the PSL-IV and an increase on the Visual Analog Scale (VAS) Fear of at least 25 mm.
- 3. BMI of 18-32 kg/m₂ (inclusive).
- 4. Non-smoker for at least 3 months.

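### The stable-trait analysis (8.9.4) compares the current response with an earlier one that, on the natural reading, was used to select the subjects, so regression to the mean looks like lost sensitivity

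*Protocol*

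**What the plan says.** Objective 4 in Protocol 1.2.5 compares PSL-IV, VAS Fear and VAS Discomfort "between these two timepoints initial assessment and years later". It looks for statistically significant differences in the frequency and intensity of panic reactions, which it reads as "indicating a maintained sensitivity or alteration to the CO2 challenge". Section 8.9.4 carries this into the analysis as the response "caused by a double (and single) vital capacity inhalation of 35% CO2/65% O2 now and some time ago".

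Two models are fixed there:
- Occurrence: "For the occurrence of PAs repeated measures logistic regression will be used with challenge number as fixed factor and subject as random factor".
- Intensity: a mixed-model ANCOVA with challenge number fixed, subject random and baseline as covariate.

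Section 4.2 admits volunteers "who have been demonstrated to be sensitive to the panicogenic effects of the CO2 challenge in previous studies". It defines sensitivity to the double-breath challenge by "PSL-IV total scores ≥4 with at least 1-point increase for at least 4 of the symptoms specified in the PSL-IV" together with "an increase on the Visual Analog Scale (VAS) Fear of at least 25 mm". Section 4.1 draws all 20 subjects from a database of about 180 such volunteers.

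**The concern.** One side of the comparison was used to choose the subjects and the other was not. PSL-IV and VAS Fear are two of the three scales behind the primary endpoint ("The primary endpoint will be based on the PSL-IV total Score, VAS Fear, and VAS Discomfort"), and both are selection scales. Among people picked because a noisy measurement exceeded a cut-off, the mean of that measurement is inflated. A fresh measurement falls back towards each person's own level although nothing has changed.

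The planned models do not remove this. A random subject effect leaves the difference between the two occasion means untouched. Baseline appears to be the pre-challenge value (8.8 defines it so for safety parameters), whereas selection was on the pre-to-post rise. The protocol mentions neither regression to the mean nor a correction for selection.

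At stake is one of four primary objectives: a stable trait could be reported as lost. The error runs in one direction only. The occurrence model may have a further problem, depending on how a panic attack is scored.

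**Working it through.** **Nothing to reproduce.** The protocol states no mean, SD, reliability, alpha or power (1.2.6 bases the sample size on no statistical consideration; 8.3 gives no power calculation). From the documents come n = 20 and the 25 mm threshold. Everything else below is an assumption.

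**1. Size under no true change (VAS Fear).** Let the earlier and current rises be bivariate normal with common mean μ, SD σ and correlation (reliability) ρ, with selection when the earlier rise is at least 25 mm. Put a = (25 − μ)/σ and λ = φ(a)/(1 − Φ(a)). Then:
- mean earlier rise in selected subjects = μ + σλ
- mean current rise = μ + ρσλ
- artefactual fall = (1 − ρ)σλ
- retention = P(both rises ≥ 25)/P(earlier rise ≥ 25); when a = 0 this equals 0.5 + arcsin(ρ)/π.

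Central case μ = 25, σ = 25, ρ = 0.6: a = 0 and λ = 0.798. The earlier mean is 25 + 25 × 0.798 = 44.9 mm. The fall is 0.4 × 25 × 0.798 = 8.0 mm, to 37.0 mm. Retention is 0.5 + 0.6435/3.1416 = 70%.

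A two-sided 5% paired t test with n = 20 stands in for the mixed model. The SD of the paired difference is σ√[(1 − ρ)²(1 + aλ − λ²) + 1 − ρ²] = 20.9 mm, so the noncentrality is 7.98/(20.9/√20) = 1.71 and the rejection rate is 37%.

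| μ | σ | ρ | Fall (mm) | Again ≥ 25 mm | Paired t rejects |
|---|---|---|---|---|---|
| 15 | 20 | 0.4 | 13.7 | 48% | 85% |
| 15 | 25 | 0.4 | 16.0 | 51% | 80% |
| 25 | 25 | 0.6 | 8.0 | 70% | 37% |
| 25 | 25 | 0.8 | 4.0 | 80% | 20% |
| 25 | 25 | 0.9 | 2.0 | 86% | 12% |
| 35 | 20 | 0.8 | 2.0 | 87% | 11% |

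Over μ 15-35, σ 20-25 and ρ 0.4-0.8 the ranges are 2-16 mm, 48-87% and 11-85%. At ρ = 0.9 over the same means and SDs they are 1.0-2.7 mm and 8-20% rejections. Retention here uses the VAS Fear threshold alone; requiring the PSL-IV threshold as well can only lower it.

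**2. Occurrence model, conditional.** Suppose a panic attack is scored by the sensitivity criterion or a looser rule. The earlier cell is then 20/20 by construction. Take 14/20 now as an example. In an ordinary logistic fit the log-odds ratio rises by 1 per iteration (5.4, 10.4, 15.4, 20.4 and 25.4 after 5, 10, 15, 20 and 25 iterations, that is, 5 per 5 iterations), while its standard error goes from 3.1 to about 66,000. With a random intercept, the profile log-likelihood climbs from −14.53 at a log-odds ratio of 1 to −12.37 at 4 and −12.22 at 8, then flattens. Its limit is 14 ln 0.7 + 6 ln 0.3 = −12.22. It never turns down, so no finite maximum likelihood estimate exists.

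**3. Like with like.** The qualifying criterion is for double breath. No earlier single-breath measurement is described, so a current single-breath result set against the earlier double-breath one would mix dose with time.

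**The case against.** The strongest reply is that the size is entirely assumed. That stands. Normality on a bounded 100 mm scale, the 5% level and the paired t test are all stand-ins, and with reliability near 0.9 or a population responding well above threshold the inflation is modest. The direction does not depend on these choices. Nor can the plan presume high reliability: measuring it is another primary objective, and 1.2.1 says its persistence over years is unknown.

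A reader might infer that the logistic model must have a 100% cell and must fail. The documents do not support that. Section 4.2 defines sensitivity; 8.9.1 to 8.9.4 give no threshold for a panic attack, and one may be set in an analysis plan not shown. A stricter rule would leave the earlier cell near 100% but not necessarily at it. The selection bias would remain.

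A reader might also infer that all primary results are affected. They are not. The single-versus-double, test-retest and tolerance analyses (8.9.1 to 8.9.3) compare visits within this trial. VAS Discomfort was not a selection variable.

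Finally, the protocol never says outright that the initial assessment is the qualifying challenge. It names no other earlier challenge, so this is the natural reading, but the point rests on it. The reference to single breath also appears in 8.9.3 and may be carried-over wording; it is a minor part of the point.

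**Conclusion.** The concern holds for the fourth primary objective, provided the initial assessment is the qualifying challenge. The comparison fixed in 1.2.5 and 8.9.4 is then biased towards lost sensitivity on PSL-IV and VAS Fear, and on VAS Discomfort only through correlation. Neither the random subject effect nor a pre-challenge covariate corrects it. Under the stated assumptions the false finding of change ranges from about one trial in nine (11%) to most trials (85%), against a nominal 5%; at reliability 0.9 in the central case it is about 12%. These figures illustrate the risk and are not the trial's error rate. The absence of a finite logistic estimate is a conditional consequence of how a panic attack is scored.

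**What to change.** Amend 8.9.4, and the reading of objective 4 in 1.2.5, as follows.

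1. State that a significant difference between the qualifying and the current response will not by itself be read as altered sensitivity.
2. For occurrence, replace the earlier-versus-current logistic regression with the proportion again meeting the sensitivity criterion at the first double-breath challenge of this trial, with an exact 95% CI. Judge it against the retention expected of a stable trait over a stated range of reliability, for example from the within-subject variation between this trial's double-breath visits. Do not judge it against 100%, which the same selection creates: 14/20 = 70% (CI 46-88%) looks like a loss against 100%, yet is what the central case predicts with no change.
3. For intensity, use an earlier double-breath challenge that played no part in selection, if the earlier studies hold one. Otherwise report the change net of expected regression to the mean. The protocol describes only the database of sensitive volunteers, so the full screening distribution may be unavailable; if so, give a sensitivity range.
4. Compare double breath with double breath only. Note that the first double challenge is visit 2, after a single-breath exposure, for half the subjects (3.1).

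This needs no new visits: wording, plus a check of what the earlier studies hold. The cost is that the result becomes an estimate resting on stated assumptions in place of a single p-value.

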In the past, various CO2 regimens have been applied to induce PAs in human populations. Although both single and double vital capacity inhalations of 35% CO2/65% O2 consistently demonstrate panicogenic effects in healthy volunteers and PD patients or their first-degree relatives, the CO2 sensitivity of both similar patient and healthy groups tend to vary between research groups. Since varying CO2 administration protocols which include both single and double vital capacity administrations are being applied across research groups, differences in CO2 sensitivity could very well be the result of unintended methodological variability. The lack of a standardized procedure to test sensitivity to CO2 therefore hampers accurate comparisons between tests performed under different protocols. A better understanding of whether a single or double breath 35% CO2/65% O2 is sufficient to induce PAs is expected to contribute to the validity of acute CO2 inhalation as tool in pathophysiological research and in early CNS drug development.

The differential response to single versus double 35% CO2 vital capacity inhalation of CO2 remains to be examined systematically to further validate it as experimental paradigm for future use. To the best of our knowledge no study has been previously published that compares single and double vital capacity 35% CO2 inhalation in a single study. Therefore, we aim to investigate the panicogenic effects of a single vs. a double vital capacity method 35% CO2 in healthy volunteers. We hypothesize that 35% CO2 double vital capacity inhalation is associated with a higher percentage of subjects experiencing a panic attack compared to single vital capacity inhalation.

Additionally, this study also seeks to systematically investigate the test-retest reliability of the CO2 inhalation challenge in healthy volunteers who are sensitive to the anxiogenic effects of CO2 inhalation. Previous research has only examined intervals of up to a few weeks, leaving it unclear whether individuals who are sensitive to the 35% CO2 inhalation challenge remain sensitive for longer periods, possibly years later. Leibold et al. (2015¹) found that a single vital capacity breath of 35% CO2 inhalation demonstrated good reliability of subjective fear in PD patients, but only used an interval of one week between inhalations. These previous studies were conducted in patients with PD, who exhibit greater sensitivity to the anxiogenic effects of the CO2 challenge compared to

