1.2.6 Statistical hypotheses and sample size

This is an observational, methodological study; therefore, the sample size is not based on statistical considerations. We've chosen a sample size of 20 participants because our current database includes 180 individuals sensitive to the panic-inducing effects of the CO2 challenge. Based on our previous experiences, selecting 20 participants from this group for the study is realistic.

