2 STUDY OBJECTIVES AND ENDPOINTS

Primary objectives	Endpoints
To investigate the difference in panic response (i.e "dose-response") between single and double vital capacity 35% CO ₂ /65% O ₂ inhalation in CO ₂ -sensitive healthy volunteers. To investigate the test-retest reliability of repeated double vital capacity 35% CO ₂ /65%	The difference in the occurrence and severity of a panic attack between the single and double vital capacity 35% CO ₂ /65% O ₂ inhalation as measured by the Panic Symptoms List-IV (PSL-IV), VAS subjective fear, and VAS discomfort. The difference in the occurrence and severity of a panic attack between the test-retest double
O2 inhalation in CO2-sensitive healthy volunteers.	vital capacity 35% CO ₂ /65% O ₂ inhalation as measured by the Panic Symptoms List-IV (PSL-IV) and VAS subjective fear, and VAS discomfort.
To investigate whether repeated double vital capacity 35% CO2/65% O2 inhalation leads to tolerance/desensitization in CO2-sensitive healthy volunteers.	The difference in the occurrence and severity of a panic attack in the repeated 35% CO ₂ /65% O ₂ inhalation as measured by the Panic Symptoms List-IV (PSL-IV), VAS subjective fear, and VAS discomfort.
To establish whether CO2 sensitivity represents a stable trait phenomenon in CO2-sensitive healthy volunteers.	The difference in the occurrence and severity of a panic attack in the repeated 35% CO ₂ /65% O ₂ inhalation as measured by the Panic Symptoms List-IV (PSL-IV), VAS subjective fear, and VAS discomfort.
Secondary objectives	Endpoints
Explore the effects of single and (repeated) double breath 35% CO ₂ /65% O ₂ on heart rate and blood pressure in CO ₂ -sensitive healthy volunteers.	Difference in mean change from pre-CO2 to post-CO2 challenge in vital sign measurements (systolic blood pressure, diastolic blood pressure, heart rate).
Explore the effects of single and (repeated) double breath 35% CO2/65% O2 on neuro-endocrine mediated autonomic nervous system activation and orexin/hypocretin release in CO2-sensitive healthy volunteers.	Differences in plasma ACTH, prolactin, orexin-1 and cortisol, and saliva amylase and cortisol from pre-CO2 to post-CO2 challenge.
To explore the relationship between baseline personality and temperament characteristics and individual response to CO2 in CO2-sensitive healthy volunteers.	Dutch Personality Questionnaire (DPQ), Cloninger Temperament Character Inventory (TCI), and Spielberger State-Trait Anxiety Inventory (STAI)

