4 STUDY POPULATION

4.1 Subject population

A study population of healthy volunteers who have been demonstrated to be sensitive to the panicogenic effects of the CO2 challenge between the age of 18 and 65. The CO2 challenge has been the subject of two studies conducted by CHDR (1614 and 1935), resulting in a database of approximately 180 healthy volunteers. For the purposes of this study, we aim to recruit 20 out of the known 180 CO2 sensitive participants.

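### Objective 4 re-tests only prior responders against their own earlier result, so it can show persistence of CO2 sensitivity but cannot by itself establish a stable trait

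*Protocol*

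**What the plan says.** One of the four primary objectives in Protocol section 2 is "To establish whether CO2 sensitivity represents a stable trait phenomenon in CO2-sensitive healthy volunteers".

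Only earlier responders can enter. Section 4.2 admits volunteers "who have been demonstrated to be sensitive to the panicogenic effects of the CO2 challenge in previous studies". It defines sensitivity at a double-breath challenge as "PSL-IV total scores ≥4 with at least 1-point increase for at least 4 of the symptoms specified in the PSL-IV", together with a rise of at least 25 mm on VAS Fear. Section 4.1 draws them from studies 1614 and 1935: "we aim to recruit 20 out of the known 180 CO2 sensitive participants".

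The comparison is within these people. Section 8.9.4 takes panic attacks "caused by a double (and single) vital capacity inhalation of 35% CO2/65% O2 now and some time ago" and models challenge number, with subject as a random factor. Section 1.2.5 (item 4) looks for statistically significant differences between the initial assessment and years later, "indicating a maintained sensitivity or alteration to the CO2 challenge".

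The protocol gives no response rate for unselected volunteers, no group of earlier non-responders and no reference proportion. On numbers, section 1.2.6 says that "the sample size is not based on statistical considerations".

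**The concern.** A claim that sensitivity is a trait says more than that some people respond twice. It says that a positive test tells you something about the person, so that someone who responded before is more likely to respond again than a volunteer taken at random. To show this, the re-test rate in prior responders has to be set against the rate in people not selected for responding.

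The plan sets it only against the same people's earlier result, which the entry criterion makes positive for everyone. A constant cannot be shown to predict anything within the sample. A high re-test rate could mean a stable characteristic, or that most volunteers respond to a double breath on most occasions. A non-significant difference between now and then fits both, yet section 1.2.5 would take it as maintained sensitivity. At stake is whether a primary objective ends in a conclusion that its data can support.

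**Working it through.** The plan has no figure of its own to reproduce: section 8.3 marks the power calculation as not applicable.

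**Inputs.** From the protocol: n = 20, and an earlier result of 20/20 by selection. The second assumes that a panic attack is scored by inclusion criterion 2, since the protocol gives no separate definition of occurrence. Assumed: two-sided alpha 0.05 (one-sided 0.025 against a reference rate), and an unselected response rate p from 30% to 80%.

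**Step 1: which counts would read as no change.** I use an exact paired (McNemar) test in place of the planned logistic regression. With every earlier result positive, an ordinary logistic fit has no finite estimate for the change (Wald p about 0.999 for 6, 10, 15 or 18 responders now), so it is no use as a yardstick. If k of 20 respond now, all 20 − k discordant pairs go one way and p = 2 × 0.5^(20 − k).
- k = 15: 2 × 0.5^5 = 0.0625, not significant.
- k = 14: 2 × 0.5^6 = 0.031, significant.

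So 15 or more of 20 would read as maintained sensitivity.

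**Step 2: how often that happens with no trait.** If everyone responds with the same probability p on every occasion, the count is binomial(20, p):

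| Assumed p | P(15 or more of 20) |
|---|---|
| 40% | 0.002 |
| 50% | 0.021 |
| 60% | 0.126 |
| 70% | 0.416 |
| 80% | 0.804 |

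**Step 3: why the data cannot settle it.** With base rate m and between-occasion correlation r, the expected re-test rate in prior responders is m + r(1 − m). A re-test rate of 75% arises from m = 75% with r = 0. It also arises from m = 30% with r = (0.75 − 0.30)/(1 − 0.30) = 0.64. Re-testing responders alone gives the left-hand side only. Precision is limited too: 15/20 has an exact 95% CI of 0.51 to 0.91, and even 20/20 has a lower limit of 0.83 (0.025^(1/20)).

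**Step 4: what a reference rate would allow.** Smallest count that exceeds a reference p0 at exact one-sided alpha of at most 0.025, and power if the true re-test rate is 90%:

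| p0 | Count needed | Power |
|---|---|---|
| 30% | 11 | >0.999 |
| 40% | 13 | >0.999 |
| 50% | 15 | 0.99 |
| 60% | 17 | 0.87 |
| 70% | 19 | 0.39 |
| 80% | 20 | 0.12 |

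These treat p0 as known exactly. Sampling error in the reference lowers the power.

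**The case against.** The narrower aim in section 1.2.5 is persistence of sensitivity in people already known to be sensitive, and that can be described without a reference group. This stands. It supports a conclusion about persistence, but not the word trait in section 2. The qualifier that the objective concerns CO2-sensitive volunteers does not help, because restricting to responders is what removes the comparison.

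The size depends on a rate that the protocol does not give. A reader might infer a high one from the statement in section 1.1 that both inhalations "consistently demonstrate panicogenic effects in healthy volunteers". That sentence also covers patients and relatives, says that sensitivity varies between research groups, and gives no share of volunteers who meet the joint PSL-IV and VAS Fear rule. A high rate is possible but not documented.

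A reader might also suppose that 14 of 20 would pass as stable. On the exact paired test it would not (p = 0.031): section 1.2.5 would call it alteration.

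The intensity analysis is no firmer ground for a stronger claim. Suppose VAS Fear has no stability, SD 25 mm and a mean rise of 25, 30, 35 or 40 mm (base rates 50, 58, 66, 73%). A paired t-test with one present value is then non-significant in about 16, 33, 50 and 65% of simulated trials. Averaging the four double challenges as independent values gives about 0.3, 4, 17 and 39%. Section 8.9.4 does not fix how many challenges enter, and correlated weekly responses would shrink that gain, so neither set is the plan's error rate.

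Nor does the design lean only towards a false trait. Selection at a threshold brings regression to the mean, which can make a real trait look as if it had faded. Last, a reference rate could stand in an analysis plan not shown here, but the population, the contrast and the reading rule are fixed in the protocol.

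**Conclusion.** The point holds in a limited form. The comparison in section 8.9.4, read as section 1.2.5 reads it, can show persistence among prior responders. It cannot separate a stable trait from a high general response rate. On the exact paired test, the chance that a no-trait population would give a result read as maintained sensitivity is 0.02 at an unselected rate of 50%, 0.13 at 60%, 0.42 at 70% and 0.80 at 80%. At 40% or below it is negligible. These figures assume scoring by inclusion criterion 2, one present result per person and equal response probabilities. The protocol does not say where in the range the true rate lies, so it does not support the inference that a false trait claim is likely. It supports only that the plan cannot rule one out.

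**What to change.** In section 8.9.4, make the lead result the proportion of the 20 who meet inclusion criterion 2 at their first double challenge in this trial, with an exact 95% CI. State that a non-significant now-versus-then test will not be read as stability.

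If the screening denominators of studies 1614 and 1935 can be recovered, show beside it the share of all volunteers who met the same criterion at their first double-breath challenge, with its own CI. Claim a trait only if the re-test proportion exceeds that share after allowing for uncertainty in both. Section 4.1 mentions a database of about 180 sensitive volunteers but no count of all those tested, so availability has to be checked. The comparison is also imperfect: the reference is a first exposure, whereas these subjects have been exposed before, and half will have had a single-breath visit a week earlier.

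If the denominators are not available, limit the conclusion to persistence of sensitivity among prior responders.

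The cost is a records search, one or two proportions with intervals and a few lines of text, with no added subjects or visits. Section 9.5.1 classes a change of statistical analysis as non-substantial. The downside is that a trait claim becomes harder to make. At a base rate of about 70% or more, 20 subjects leave the question open (power 0.39 or less at a true re-test rate of 90%). That outcome must be reported as inconclusive, not as evidence that there is no trait.
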